#### **Summary**

**Study title**: Behaviour Change Interventions to Improve Medication Adherence in Patients with Cardiac Disease.

**Protocol version**: 1

#### **Objectives**

#### Primary objective:

- To detect medication non adherence.
- To explore individual, behavioural and environmental factors that hinder medication adherence.

#### **Secondary objectives:**

• To examine the effectiveness of a multifaceted intervention comprising motivational interviewing techniques plus text message reminders to enhance adherence to cardiac medications.

**Study design**: Sequential mixed methods with nested pilot Randomised Controlled Trial (RCT).

Planned sample size: 28 participants.

#### **Selection criteria:**

- 1.18 years of age or older.
- 2. Diagnosed with cardiac disease by their physician and referred to the cardiac rehabilitation program at POWH.
- 3. Prescribed at least one cardio-protective medication at least 7 days prior to recruitment.
- 4. Must also be able to speak, read and understand English.
- 5. Own a personal mobile phone, and be able to receive and reply to phone calls and text messages.

#### **Exclusion Criterion:**

1. Clinically identified or formally diagnosed with cognitive impairment; blind or deaf.

#### Study procedure

**Statistical considerations:** The sample will be selected from a consecutive cohort of patients referred to cardiac rehabilitation for cardiac disease secondary prevention.

#### Sample size calculation:

- With alpha = 0.05 (2sided), power= 0.80 (beta= 0.20).
- With consecutive sampling and allowing for 50% loss to follow-up.
- A sample size of 28 participants for both groups will be recruited (Ma et al. 2014).

**Recruitment and screening**: Patients referred to Cardiac Rehabilitation at POWH will be screened by the Clinical Nurse Consultant (CNC) as they attend their first session. For Phases One and Two, eligible patients will:

- Have an established diagnosis of cardiac disease by their physician;
- Will have been prescribed at least one cardio-protective medication at least 7 days prior to recruitment;
- They must have primary responsibility for taking their medication themselves (i.e. whilst a carer may play a role in supporting or promoting medication taking, they should not be identified as being accountable for ensuring the patient's adherence to their medication schedule);
- Patients must not be clinically judged as affected by cognitive impairment and must be able to speak, read and understand English, own a personal mobile phone, and be able to receive and reply to phone calls and text messages.

All patients recruited will complete a paper-based survey (phase one) and a brief face to face interview (phase two).

For the Pilot Trial Phase:

Participants identified as 'non-adherent' to at least one of their cardiac medications, based on the
result of exploratory phases of the study (survey and interview), will be invited to participate in
the final pilot randomised trial phase.

Patients recruited to the pilot trial phase will be randomly allocated to either an intervention or control arm.

**Intervention:** Participants in the intervention group will receive usual care plus behavioural counselling about medication adherence using motivational interviewing (MINT) techniques and text message reminders.

**Control group**: will receive the usual cardiac rehabilitation program.

**Analysis plan:** Phase one: Descriptive statistics; Phase two: thematic analysis; Pilot trial Phase: descriptive statistics and inferential data analysis.

**Duration of the study:** The total duration of the study will be 12 months (six months for recruitment and six months participation for each participant recruited).

Version 2: 20/05/2016 ------ Page 4 of 42

#### 1. BACKGROUND

#### 1.1. DISEASE BACKGROUND

In recent decades coronary heart disease (CHD) has become a global health concern (Zhu et al., 2015). The prevalence of cardiovascular disease (CVD) is rapidly rising worldwide because of changing lifestyles adding challenges for both patients and healthcare providers (Hauptman, 2008). CVD has emerged as a leading cause of death and disability worldwide, particularly in developing countries (Gaziano, 2005). The prevalence of the disease increases with age and affects one in six Australians, ranging from 35% of those aged 55-64 years to 62% of those aged 75 years and over (Australian Bureau of Statistics, 2012). The prevalence of CVD increases with the presence of one or more major risk factors, including: family history, hypercholesterolemia, hypertension, diabetes, smoking, obesity, and physical inactivity (Australian Bureau of Statistics, 2012). Although a large proportion of CVD is preventable, the incidence of the disease remains high. In Australia, as in other developed countries, the prevalence and incidence of CVD has continued to increase in recent years regardless of advances in medical technologies and development of prevention programs (Australian Bureau of Statistics, 2012). Cardiovascular disease imposes significant burden on individuals and the health care systems in this country. It is the single greatest cause of death in Australia, accounting for the deaths of 21,867 males and 23,755 females in 2011 (Australian Institute of Health Welfare, 2014). In Australia, CVD is also the main reason of rehospitalisation, accounting for 524,000 hospitalisations in 2011/12 (Australian Institute of Health Welfare, 2014). According to AIHW (2010), CVD was responsible for 16% of the total burden of all diseases, which translated to AU\$5.94 billion and equated to 11% of total health expenditure of Australia in 2004-2005 (Australian Institute of Health and Welfare, 2010).

Adherence to medications is a serious challenge, particularly in patients with chronic conditions such as cardiac disease who often need to take multiple medications for long periods (World Health Organisation, 2003). Numerous types of cardiac medication are available and have been proven effective for symptom management and slowing the progression of CVD. Multiple long-established and newer medications, such as angiotensin converting enzyme [ACE] inhibitors, β-blocking agents, aldosterone inhibitors, aspirin, statins and warfarin are prescribed to inhibit the progress of the disease and control its symptoms (Albert, 2008, Wu et al., 2008). The risk of mortality and morbidity in patients with cardiac disease increases if adherence to prescribed medication is poor (Hope et al., 2004). Medication non-adherence in patients with cardiac

Version 2: 20/05/2016 ----- Page 6 of 42

conditions varies between 33% to more than 50% (Li et al., 2012, Munger et al., 2007, Shah et al., 2013), contributing to increased numbers of cardiovascular-related Emergency Department (ED) visits, rehospitalisation, poor health and well-being, augmented healthcare costs and risk of death ((Ashton et al., 1995, Mukhtar et al., 2014, Munger et al., 2007).

#### 1.2. RATIONALE FOR PERFORMING THE STUDY

This proposed project aims to fill in the gap in the literature by developing and testing the effectiveness of an intervention designed to enhance adherence to cardio-protective medication in cardiac patients. This study will focus on cardiac patients with low-adherence, and apply adherence interventions to improve adherence in these patients. Appropriately designed interventions that utilise multiple approaches such as motivational interviewing targeting behaviour change, and reinforcing behaviours with text message strategies are likely to significantly increase medication adherence in cardiac patients ([name] et al. under review). This study aims to evaluate the effectiveness of a theory based intervention on medication adherence in a robust pilot trial using RCT design. If effective, this nurse-led intervention could be implemented in cardiac rehabilitation programs in Australia to help improve patient adherence and enhance the effects of medical therapy and result in improved patient and disease outcomes, such as reduction in disease symptoms, recurrent cardiac events, rehospitalisation and mortality.

Non-adherence is a multifactorial phenomenon, affected by socio-economic status, health systems, disease states, pharmacological therapies and patient beliefs (Sabaté, 2003). For the purpose of this study, non-adherence is defined as "taking less than 80% of prescribed doses that can also include taking too many doses" (Nieuwlaat et al., 2014). In order to reduce the risk of recurrent cardiac events, it is important to identify factors that influence adherence and tailor supportive interventions that can help achieve improvement in patients adherence to their medication regimens (Munger et al., 2007).

#### **Hypothesis**

The study hypothesis is that motivational interviewing (MINT) counselling and text message reminders delivered in an outpatient setting in addition to standard care will enhance maintenance of medication adherence in cardiac patients compared to standard care alone.

Underpinning evidence and assumptions of the hypothesis are that:

1) A high proportion of patients fail to adhere to their cardiovascular medication regimens.

Version 2: 20/05/2016 ------ Page 7 of 42

- 2) Medication adherence self-efficacy, patient beliefs and lack of social support are factors associated with non- adherence to medication.
- 3) High quality evidence supports use of multifaceted interventions comprised of motivational interviewing (MINT) counselling combined with text messaging reminders to improve medication adherence.

#### 2. STUDY OBJECTIVES

#### 2.1. PRIMARY OBJECTIVES (PHASE 1 AND 2) AND OUTCOMES

- 1. To determine self-reported adherence or non-adherence to prescribed cardiac medications in cardiac patient referred to a cardiac rehabilitation program. The outcome will be self-reported medication adherence/non-adherence.
- To explore individual, behavioural and environmental factors that affect adherence to cardiac medications. The outcome will be identification of factors that influence adherence to medications.

#### 2.2. SECONDARY OBJECTIVE (PILOT TRIAL PHASE) AND OUTCOMES

To conduct pilot-testing of the hypothesis that, compared to standard care alone, standard care plus a multifaceted intervention comprising motivational interviewing techniques and text message reminders will enhance cardiac medication adherence among cardiac patients referred to attend cardiac rehabilitation program. The primary outcome will be medication adherence/non-adherence rate at six months/ change in medication adherence between baseline and 6 months scores.

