Non-adherence to medications will be assessed by the **Medication Adherence Questionnaire** (**MAQ**) designed to measure medication adherence behaviour and barriers such as forgetfulness, carelessness, adverse effects and efficacy. MAQ includes simple four-item dichotomous questions, scoring one point for each yes response; total scores are categorised as: 0 point indicating high; 1-2 points medium, and 3-4 points low medication adherence behaviour.

The Adherence to Refills and Medications Scale (ARMS) will be used to determine the patient medication adherence behaviour in terms of self-regulation. The ARMS comprises a 12-item scale with the first 8-item medication taking subscale assessing correct self-administration ability for the prescribed regimen. The next 4-item prescription refill subscale assesses the patient's ability to refill medications on schedule. Each item is scored on a four point scale ranging from l=

Version 2: 20/05/2016 ----- Page 15 of 42

none of the time to 4= all the time. The higher numbers on the scale demonstrate patient's better ability to refill medications on schedule.

The Belief about Medicine Questionnaire (BaMQ) elicits information on patients' beliefs about their medicines where they may relate to adherence. It identifies whether the patient holds beliefs that their medicines are necessary or if they have concerns about their medicines. The study will use the short version of the BaMQ (the 8-item) developed by Horne et al., 1999. This version is composed of four subscales containing two items each, and assessing: General Harm; General Overuse; Specific Necessity; and Specific Concerns. Respondents indicate their degree of agreement with each statement on a five point Likert scale, ranging from l=strongly disagree to 5=strongly agree. The lower numbers on the scale demonstrate the patient's strong beliefs about taking medications. Scores are summed to give a total score, with higher scores indicating more positive beliefs. The focus of the BaMQ, is identification of barriers to medication adherence, contributing to comprehensive evaluation of the drivers behind medication adherence.

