#### 5.4. RECRUITMENT AND SCREENING

Patients identified as 'non-adherent' to at least one of their cardiac medications based on the result of exploratory phases (Phase One and Phase Two) will be invited to participate in this pilot

Version 2: 20/05/2016 ----- Page 18 of 42

randomised trial phase. Participants will be assessed as adherent or non-adherent based on the response to the Medication Adherence Questionnaire (MAQ). Patient with a total score of 1-2 will be considered as "adherent", and those with a total score of 3-4 as "non-adherent". At conclusion of the interview (Phase Two), eligible participants who are identified as "non-adherent" will be informed about Phase 3, the pilot RCT trial phase.

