Pilot trial phase: The researcher will compare the two groups at baseline. Data will be analysed according to intention to treat analysis using statistical methods based on the study hypothesis. The primary outcome will be medication adherence/non-adherence at six months and changes in adherence scores since baseline. Descriptive statistical analyses will be used to illustrate the participants' baseline characteristics. The independent samples t-test will be used to compare the mean medication adherence questionnaire scores (MSSS, MAQ, ARMS, BaMQ, and MASER-R) between the intervention and usual care groups. Paired samples t-test analysis will be used to test within groups differences on medication adherence questionnaire scores (MSSS, MAQ, ARMS, BaMQ, and MASER-R). Logistic regression analysis will be applied to identify variables that significantly influence adherence to medications (i.e. self-efficacy, beliefs, level of confidence, and social support).

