27. When you feel well				

Version 2: 20/05/2016 ------ Page 30 of 42

28. If they make you want to urinate while away from home				
Please rate how sure you are that you can carry out the following task:				
29. Make taking your medications part of your routine				

Version 2: 20/05/2016 ------ Page 31 of 42

There are no right or wrong answers. For each of the beliefs listed below, please rate how you agree or disagree about your beliefs of taking medications.

Items	Strongl y Agree	Agree	Uncertai n	Disagree	Strongly Disagree
30. My health, at present, depends on my medicines					
31. My medicines protect me from becoming worse					
32. My medicines disrupt my life					
33. I sometimes worry about long-term effects of my medicines					
34. Doctors use too many medicines					
35. People who take medicines should stop their treatment for a while every now and again					
36. Most medicines are addictive					
37. Medicines do more harm than good					

For the next set of questions, please indicate how often people may have helped you in the various ways described during the PAST THREE MONTHS.

How often has someone in the past three months?

Questions	Never	Rarely	Sometime s	Often	Very often
38. Helped you monitor your symptoms and medication side effects?					
39. Reminded you to take your medications?					
40. Picked up your cardiac medication prescriptions for you?					
41. Helped you understand information about your medications?					
42. Checked in with you about your medications?					
43. Encouraged you to talk to your doctor about your medications when you have questions or problems?					
44. Helped you to believe you can take your medications as prescribed?					
45. Called you specifically to ask how you were doing with your cardiac medications?					

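### The pilot trial's primary outcome is two endpoints with no instrument tied to either, five scales are tested with none primary, and no between-arm comparison of the adherence rate is stated

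*Protocol*

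**What the plan says.** The primary outcome of the pilot trial is given twice in the protocol. Section 2.2: "The primary outcome will be medication adherence/non-adherence rate at six months/ change in medication adherence between baseline and 6 months scores". Section 9, pilot trial paragraph: "The primary outcome will be medication adherence/non-adherence at six months and changes in adherence scores since baseline". Neither sentence names a questionnaire.

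The two arms are compared in section 9 by this sentence, whose closing words name the arms: "The independent samples t-test will be used to compare the mean medication adherence questionnaire scores (MSSS, MAQ, ARMS, BaMQ, and MASER-R) between". No scale is singled out, and the sentence does not say whether six-month scores or changes are compared. Change is tested only within groups, by paired t-test.

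The only analysis with adherence status as its outcome is this: "Logistic regression analysis will be applied to identify variables that significantly influence adherence to medications". The variables listed for it are self-efficacy, beliefs, level of confidence and social support. Randomised arm is not among them.

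Other sections bear on which instrument is meant:

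- Section 5.3.1 gives the MAQ as the measure of non-adherence: "MAQ includes simple four-item dichotomous questions, scoring one point for each yes response". A total of 0 is high, 1–2 medium and 3–4 low adherence.
- Section 5.4 uses the MAQ for trial entry, with 1–2 adherent and 3–4 non-adherent. A score of 0 is not assigned.
- Section 1.2 defines non-adherence by a threshold of 80% of prescribed doses, which none of the five scales measures.
- Sections 3.3 and 8 power the trial on group means of 29.72 and 25.30 (difference 4.42, SD 3.285) without naming the scale.

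**The concern.** A rate and a change score are different endpoints. They have different tests and different sample-size needs, and they can disagree. With both called primary and no instrument attached, the choice of what counts as the trial's result is left open until the data are in. The five t-tests widen that choice. Three of those scales (BaMQ, MASES-R, MSSS) measure beliefs, self-efficacy and social support, which the hypothesis text and the instrument table treat as influences on adherence.

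The endpoint named first, the six-month rate, gets no stated comparison between arms. Followed as written, the plan could end without a randomised answer on it.

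**Working it through.** **1. The plan's own figure.** Section 8 uses n = 2(a+b)²σ²/(μ₁−μ₂)². With a = 1.96, b = 0.842, σ = 3.285 and a difference of 29.72 − 25.30 = 4.42:

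n = 2 × 2.802² × 3.285² / 4.42² = 169.448 / 19.5364 = 8.67, so 9 per group.

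This reproduces. It is a calculation for a continuous score (standardised difference 4.42/3.285 = 1.35), so it gives no basis for the binary rate.

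**2. Which scale could be the powered outcome?** Ranges follow from the scoring in section 5.3.1.

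| Scale | Range as scored | Can hold 29.72 and 25.30? | Measures |
|---|---|---|---|
| MAQ | 4 × (0–1) = 0–4 | No; 4.42 exceeds the whole range | Adherence |
| ARMS | 12 × (1–4) = 12–48 | Yes | Adherence |
| BaMQ total | 8 × (1–5) = 8–40 | Yes | Beliefs |
| MASES-R | item mean, 0–3 | No | Self-efficacy |
| MSSS | item mean, 0–4 | No | Social support |

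The instrument that classifies adherence therefore cannot be the powered one. The rate (if it is MAQ-based) and the powered score are different endpoints. Only ARMS both fits the powered values and measures adherence. The protocol does not say that the values came from ARMS, only that they came from a cited trial.

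**3. Size of the multiplicity.** Assume each between-arm test is two-sided at 0.05 and any could be claimed as the result. For k independent tests, P(at least one false positive) = 1 − 0.95^k.

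- Two adherence scales (MAQ, ARMS): 1 − 0.95² = 0.0975, about 10%. At an assumed correlation of 0.5 it is about 9%.
- All five scales: 1 − 0.95⁵ = 0.226, about 23%. Simulation at an assumed correlation of 0.5 gives about 18–19%.

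The 0.05 level is itself inferred. The trial-phase paragraph states no threshold. It comes from the sample-size text, and the p-value rule in section 9 sits under Phase one.

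**4. The rate at the planned size.** The protocol gives no adherence rates, so these are assumptions. With 9 completers per arm, power by Fisher's exact test is 15% for 20% vs 50%, 14% for 30% vs 60%, 28% for 20% vs 60%, and 44% for 30% vs 80%. The rate is not a workable primary at this size.

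**5. ARMS scoring direction.** Section 5.3.1 says higher ARMS scores are better. In Appendix A, the ARMS items (5–16) mostly ask how often doses or refills are missed, so a higher answer is worse. Item 16, on planning refills ahead, runs the other way. An ARMS total cannot be interpreted until this is reconciled.

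**The case against.** **The label.** Section 9 speaks of questionnaire scores, and the whole survey pack in Appendix A carries an adherence-questionnaire title, so the phrase may simply name the pack. Elsewhere the protocol keeps beliefs, self-efficacy and support apart from adherence, and section 9 itself uses them as predictors. This stands. A reader might infer that the plan declares all five scales to be adherence outcomes and quote 23% as its error rate. The text does not go that far. About 10% is the figure for the two adherence scales, and 23% is an upper bound.

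**The MAQ is named.** True for the survey and for trial entry. What is missing is a link to the six-month outcome. A reader might fill that gap by taking the MAQ as primary, but the powered difference rules it out.

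**MSSS and the intervention.** Items such as "39. Reminded you to take your medications", 42 (checking in) and 45 (calling) resemble the study's own contacts. A reader might conclude that MSSS must rise in the intervention arm. The documents support only that it can. Some of the eight items are of this kind, recall covers three months when texts are weekly, calls go to those who do not respond or answer no, and participants may not count study contacts.

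**The regression.** The variable list does not prove that arm would be left out of a fitted model, and a reader might also want a false-positive rate for the regression. The protocol does not settle how many distinct predictors there are. MASES-R is the only instrument described for self-efficacy, and its items are rated as confidence, so two of the four listed variables appear to share one measure.

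**It is a pilot, and an SAP may exist.** Multiplicity handling and full model specification can be left to an SAP, and their absence is not the point. The double primary and the unranked test list are fixed in the protocol, and an SAP would have to override them. Sections 1.2 and 3.1 present the pilot as a test of effectiveness, and section 3.3 powers it at 80%, so one defined primary matters.

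**Conclusion.** The point holds in this form. The protocol makes a binary six-month rate and a change in scores jointly primary and ties no instrument to either. It tests five scales between arms with none designated primary, and it states no between-arm comparison of the rate. The powered difference cannot occur on the MAQ, so the ambiguity cannot be resolved by reading the MAQ into the outcome.

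The inflation in false positives is about 10% for the two adherence scales and at most about 23% for all five. This assumes tests at 0.05 each, freedom to claim any of them, and independence. Positive correlation lowers both figures. The finding does not depend on MSSS being certain to rise, or on any error rate for the predictor regression.

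**What to change.** - **Sections 2.2 and 9:** name one primary, the between-arm difference in six-month ARMS total adjusted for baseline ARMS. State in sections 3.3 and 8 which scale the 4.42 points refer to.
- **Section 5.3.1 and Appendix A, first:** reconcile the ARMS scoring direction, including item 16.
- **Adherence rate:** make the MAQ-based rate secondary, compared between arms as a risk difference with an exact confidence interval. Class a score of 0 as adherent, in line with section 5.3.1, where 0 is high adherence.
- **BaMQ, MASES-R, MSSS:** report as secondary process measures, not adherence outcomes. Note that MSSS items 39, 42 and 45 can pick up the study's own texts and calls. Do not change the MSSS wording at six months only, because that would break comparability with baseline.
- **Trial-phase predictor regression:** label it exploratory and enter MASES-R once.

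The cost is protocol wording, and fewer results can be called primary. With a single continuous primary, the stated 9 completers per group stands by the protocol's own formula. Keeping all five tests with a Bonferroni level of 0.01 would instead need 13 per group, and 9 would give 61% power.
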